1. INTRODUCTION

1.1 Background

NAVIFY Oncology Hub is a platform that aggregates and organizes disparate data into an intuitive, longitudinal view of the patient's cancer care journey.

The platform is designed to optimize and support oncology workflows and decision-making by providing quick access to the most relevant data in one place, so that providers can make decisions more efficiently and collaborate more seamlessly.

Clinical workflow is critical for the efficient and safe delivery of patient care. In most healthcare settings, clinical workflow is highly complex, and reflects the multidisciplinary collaboration and communication required of most clinical tasks. Studies have demonstrated a positive association between leveraging health information technology workflow tools for care coordination and patient engagement, and improved process quality metrics in preventive screening, diabetes control, as well as maternal and child health (Kruse & Bean 2018; Kranz et al. 2018). Embedded decision support tools have also been proven to improve the performance of risk assessments conducted by providers, as well as enhance patient safety and decrease mortality (Chaudhry et al. 2006; Wells et al. 2008; Jones et al. 2014; Campanella et al. 2015).

This research protocol builds on previous work that validated clinical simulation methods as a means for clinicians to generate useful insights during the testing and development of digital health tools (Gardner et al. 2020).

1.2 Study Rationale

This work seeks to understand current clinical workflow practice and validate use cases for NAVIFY Oncology Hub.

The main purpose of NAVIFY Oncology Hub is to enhance clinical and operational effectiveness, from diagnostic workup to treatment planning and management. This might free up providers' time and capacity to provide better and more personalized care to patients.

Accordingly, this study aims to test the ability of NAVIFY Oncology Hub to increase the work efficiency of oncologists and reduce the cognitive burden/mental fatigue associated with patient care and decision-making.

The insights generated will be used to guide the development of NAVIFY Oncology Hub and optimise user experience, as well as provide a better understanding of the opportunities for it to have maximal impact in the decision-making process.

2. STUDY OBJECTIVES

This work seeks to generate evidence and insights that will inform product development and support go-to-market activities for NAVIFY Oncology Hub.

2.1 Study objectives

This work is designed as a 2-phase study.

Phase 1 objectives (semi-structured interviews):

- 1. Understand current clinical practice
- 2. Validate use cases of NAVIFY Oncology Hub

Phase 2 objectives (simulation study):

- 1. To assess the usability of NAVIFY Oncology Hub
- 2. To assess the efficiency of using NAVIFY Oncology Hub
- 3. To assess the mental effort required with using NAVIFY Oncology Hub
- 4. To gather feedback on the study methods

3. STUDY DESIGN

This study will run over 2 phases.

Phase 1 (semi-structured interviews) – We will conduct a total of 12 semi-structured interviews with 12 US oncologists. These interviews will seek to:

(i) Understand incumbent clinical practice for activities that NAVIFY Oncology Hub is seeking to improve, for example, accessing cancer patient data, and care coordination.
(ii) Validate use cases of NAVIFY Oncology Hub and its perceived benefits, for example, reducing cognitive burden, increasing shared decision-making, etc.

There are 5 proposed use cases for NAVIFY Oncology Hub:

- 1) New patient consultation
- 2) Returning patient, follow-up visit
- 3) Cross team care coordination
- 4) Facilitating patient discussions and education
- 5) Enrichment of the patient record

The results from Phase 1 will inform potential adjustments to simulation study procedures for Phase 2, such as the duration of the simulation sessions.

An interview guide has been provided in Appendix B.

Phase 2 (simulation study) – This phase of the study will have approximately 30 US oncologists. We will first conduct a small number of simulation sessions (3-5) to validate study methods and data collection procedures. Study methods may then be refined before conducting simulation sessions with a larger number of participants (approx. 25).

In this phase, each participant will participate in a 90-minute simulation session in which they will use NAVIFY Oncology Hub to review synthetic patient cases. Participants will be tasked with reviewing the cases as if they were preparing to see a patient in a real clinical setting. This task will involve searching for, identifying, reviewing and synthesizing relevant clinical information (demographic information, pathology reports,

> Protocol No: HLR-NOH-001 Version No: v2.0 Date: 6 May 2022

clinical course, etc.) that supports decision-making. As such, this task is meant to simulate the same activities they would perform in their typical practice before inviting a patient into the clinic room for a consultation, and will permit this study to examine the usage of NAVIFY Oncology Hub on those activities.

Ultimately, the aim of the study is to investigate how NAVIFY Oncology Hub improves efficiency and reduces cognitive burden associated with reviewing and synthesizing patient information, and having participants engage with the platform requires them to go through those tasks.

4. STUDY POPULATION

US adults, age 18 and older, fluent in written and spoken English who are board-certified oncologists with an MD/DO degree from an accredited institution. Participants will be affiliated with a healthcare institution where they are an active member of a tumor board and spend at least 50% of their time in clinical practice. We will recruit a mix (as equal as possible) of oncologists based in a community setting and those based in larger academic centers. Because prior work demonstrates an influence of oncologist experience on treatment outcomes (Go et al. 2015; Huntington et al. 2018; Shanafelt et al. 2012), we will include a mix of participants in terms of experience and type of practice institution. All participants will perform at least five clinical sessions per week.

5. STUDY PROCEDURES

5.1 Recruitment

We will recruit potential participants working in the United States for a remote study. Potential participants will be identified and recruited by the Prova Health team through email and phone. For those who meet criteria and agree to participate, a digital or written informed consent will be obtained. They will then be scheduled for the remote simulation session.

5.2 Conduct of semi-structured interviews

Semi-structured interviews: Participants will participate in a 60-minute remote (e.g., online) interview. A topic guide for the interview can be viewed at Appendix B. During scheduling, participants will be given a link to use to join the session. This link will take them to a video conference call hosted through Google Meet. The interviewer will use Google Meet to record the participant's audio. At the conclusion of the session, participants will be compensated.

5.3 Conduct of simulation sessions

Simulation sessions: Participants will participate in a 90-minute remote (e.g., online) simulation session. During scheduling, participants will be given a link to use to join the session. This link will take them to a video conference call hosted through Google Meet. At the session, the moderator will facilitate the session and take notes. The moderator will be a member of the Prova Health team with clinical practice

experience. At the beginning of the session, participants will be instructed to share their screen with the moderator so that participants' use of NAVIFY Oncology Hub can be recorded. The moderator will then use Google Meet to record the participant's screen. Participants will be instructed to turn off their camera to preserve anonymity while ensuring data retention. At the conclusion of the session, participants will be compensated.

Activity	Duration (mins)
Introductions and consent	5
Review of simulation session guide	5
Training on NAVIFY Oncology Hub	20
Prepare 10 cases using NAVIFY Oncology Hub	50
Post-Simulation Survey	10
Total	90

A timeline of the simulation sessions is provided below.

5.3 Ensuring fidelity during remote participation

Participants will participate in the simulation sessions remotely (e.g., using an online video conference call). To ensure data visual fidelity, we will request that participants close any other programs that involve heavy internet usage (e.g., internet browser other than the one used for participation, video conferencing software) and mute their cell phone to minimize the risk of interruption of the study. They will also be requested to use headphones for the duration of the study, to ensure all instructions are heard clearly.

The only requirements for remote participation will be a web browser and an internet connection. Participation will occur through Google Meet video conferencing software. This platform does not require that participants download anything; participants can join from a standard internet browser. During scheduling for both the training and simulation sessions, participants will be given a link to Google Meet for the session.

Prova Health will provide support to ensure internet connections and access. If the participant is removed from the video conference call, Prova Health's personnel will attempt to re-contact. If the participant's computer is no longer functional or if the participant's computer no longer has internet access, an attempt will be made by Prova Health personnel and the participant to correct the issue. If this is not successful in a reasonable amount of time (accounting for the participant's schedule and any subsequent testing sessions), the session will be terminated. If the session is terminated before the participant has begun preparing cases, the participant will be rescheduled for a new session (if they are interested in continuing to participate). This session will be treated as an entirely new session (e.g., the participant will complete all measures). However, if the participant had already begun preparing patient cases, the participant will not be rescheduled.

5.4 Case Construction

A set of 10 synthetic breast cancer patient cases will be developed by Prova Health. Cases will include history and examination findings, pathology reports, radiology reports and images (USS, mammogram, CT as applicable) and reports on tumor characteristics. The case details will be representative of a long term patient journey, inclusive of treatment lines such as adjuvant and neoadjuvant therapies.

Cases will be selected to span the range of potential case scenarios seen in typical practice. Specifically, cases will be selected to include common invasive breast cancers (eg. IDC, ILC), as well as less common invasive breast cancers (eg. inflammatory). Cases will also represent a range of cancers with different molecular subtypes, such as whether the patient is HER2 positive or negative, hormone receptor (HR) positive or negative or triple negative. Finally, cases will also reflect the presentation of patients at various stages (eg. primary diagnosis, locally and regional advanced breast cancer, recurrent breast cancer, or metastatic advanced breast cancer).

6. STUDY VARIABLES AND MEASURES

6.1 To assess the usability of NAVIFY Oncology Hub

At the end of the simulation session, some of the study's outcome measures will be collected via a **Post-Simulation Survey** (see Appendix A). The usability of NAVIFY Oncology Hub will be assessed using the System Usability Scale (SUS), a 10-item validated questionnaire for assessing the usability of websites and software applications.

In addition, useful information from a product development perspective will be collected on the Post-Simulation Survey, for example:

- Which aspects of NAVIFY Oncology Hub did you find **most useful**?
- Are there any **changes you would make to NAVIFY Oncology Hub** if you could?
- What aspects of NAVIFY Oncology Hub were **most challenging**?
- How likely would you be to use NAVIFY Oncology Hub in your typical practice?
- How **likely would you be to recommend** NAVIFY Oncology Hub to your colleagues?

The participant's screen will also be recorded using Google Meet. This will be used to corroborate moderator recordings. These recordings will also be available to the funder to provide user insights to support product development.

6.2 To assess the efficiency of using NAVIFY Oncology Hub

The Post-Simulation Survey will be used to measure the perceived efficiency of using NAVIFY Oncology Hub when compared to standard practice.

The moderator will also note the start and finish time for each case, which will permit measurement of 1) Time spent on each case, and 2) Overall session time.

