7. ANALYSIS

Thematic analysis of interview outputs will be performed by reviewing recordings from study participants in Phase 1. This analysis seeks to validate potential benefits and use cases for NAVIFY Oncology Hub, especially in areas such as accessing cancer patient data, care coordination, cognitive burden and shared decision-making.

Data from the simulation sessions will involve calculating summary descriptives (e.g., means and percentages) on case-specific endpoint measures. Counts or percentages may also be calculated on tabulated responses to survey questions to determine whether certain themes regarding the study participants' participation experience prove common across the participants and, therefore, warrant attention.

8. **REGULATORY ISSUES**

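### Is overall session time unusable as an efficiency measure because the session is planned at 90 minutes, 40 of them not case work?

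*Combined protocol and SAP*

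**What the plan says.** Efficiency is the second Phase 2 objective (section 2.1). Section 6.2 measures it by perceived efficiency on the survey and by two timed quantities. The timed ones come from the moderator's note of the start and finish of every case, "which will permit measurement of 1) Time spent on each case, and 2) Overall session time". Nothing further defines the second.

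For the session itself, section 3 says that "each participant will participate in a 90-minute simulation session in which they will use NAVIFY Oncology Hub to review synthetic patient cases". The timetable in section 5.3 (Conduct of simulation sessions) totals 90 minutes. Its rows include "Training on NAVIFY Oncology Hub" (20 minutes) and "Prepare 10 cases using NAVIFY Oncology Hub" (50 minutes). Section 5.1 schedules one session: "They will then be scheduled for the remote simulation session".

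The other section 5.3 (Ensuring fidelity during remote participation) has a sentence that reads as if there were two: "During scheduling for both the training and simulation sessions, participants will be given a link to Google Meet for the session". It also says of a call that fails partway that "if the participant had already begun preparing patient cases, the participant will not be rescheduled".

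Section 7 plans "calculating summary descriptives (e.g., means and percentages) on case-specific endpoint measures" and does not mention session time. Section 3 leaves the length of the sessions open to adjustment after Phase 1. It also begins Phase 2 with 3 to 5 sessions meant to validate methods and data collection.

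**The concern.** If the session means the whole call, as it does in sections 3 and 5.3, one of only two timed efficiency measures would be set mainly by the timetable. Forty of its 90 minutes have nothing to do with preparing cases. A participant who completed fewer cases within a fixed block would show the same session time as one who completed all 10.

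The doubt over training adds a second ambiguity. The same case work might be reported as 50 minutes (case block), 70 (call without training) or 90 (whole call).

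The plan also does not say whether case work stops at 50 minutes, or how times are used from a call that is lost after cases have begun. If slow participants were cut off, the mean time over completed cases could be distorted. At stake is the meaning of the absolute times reported for the efficiency objective.

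**Working it through.** **1. The plan's own figure.** The timetable rows in section 5.3 are introductions and consent 5, guide 5, training 20, cases 50 and survey 10.

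- Total: 5 + 5 + 20 + 50 + 10 = 90 minutes, as stated.
- Not case work: 90 − 50 = 40 minutes, or 40/90 = 44.4%.
- Planned time per case: 50/10 = 5.0 minutes.

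**2. What the named data can yield.** Section 6.2 records a start s and a finish f for each case, and nothing else. From these one can compute:

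- time per case, f − s;
- the sum of the case times;
- the span, f of the last case minus s of the first.

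The span exceeds the sum only by gaps between cases. The first three rows (5 + 5 + 20 = 30 minutes) are over before the first start, and the survey (10 minutes) follows the last finish. Neither total contains any of the 40 minutes. Both describe the block planned at 50 minutes. A figure of 90 would need the start and end of the call, which section 6.2 does not list as a source.

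**3. The 70-minute figure.** It is 90 − 20, and assumes that training moves out while every other row stays as it is. The documents give no 70-minute session. Sections 3 and 5.3 both put the simulation session at 90, and the sentence that mentions training sessions gives no duration.

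**4. Dilution.** Suppose case time fell from 5 to 4 minutes per case, a saving of 10 minutes over 10 cases. The fall would be 10/50 = 20% of the case block, 10/70 = 14% of a call without training, and 10/90 = 11% of the whole call. It would be 0% if every call ran exactly 90 minutes. These percentages describe a contrast between two conditions. Phase 2 has only one: every participant uses the Hub, and the comparison with standard practice is perceived, by survey. No planned result is diluted. The 0% also assumes a fixed call length, and the documents state no cut-off at 90 minutes. If the non-case time were constant at 40 minutes, adding it would raise the mean by 40 and leave the spread and the differences between participants, in minutes, as they were.

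**5. The planned analysis.** Section 7 summarises case-specific measures. Time per case is one of them and does not depend on what the session means. No hypothesis, sample size or decision rule uses session time.

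**6. An unstated stop.** The documents neither impose nor exclude a stop at 50 minutes. With no stop and all 10 cases done, the distortion is 0%. A simulation with a hard stop assumed lognormal case times, a within-user log SD of 0.45, a between-user log SD of 0.2 to 0.5, and a one- to two-fold speed-up over the 10 cases. The mean over all completed cases was then off by:

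| True mean per case | Distortion |
|---|---|
| 3 min | −4% to 0% |
| 5 min | −13% to 0% |
| 8 min | −21% to +6% |

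None of these inputs comes from the documents. Whatever happens, the number of cases each participant completed can be counted from the finish times already noted.

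**The case for a change.** The best case for a change is that the plan contradicts its own vocabulary. Wherever a length is given, the simulation session is the 90-minute call, so an analyst could report call length under this label and still claim to follow the plan. The screen recording, kept under section 6.1 to corroborate the moderator's notes, would supply a rough figure. Efficiency has only two timed measures, so an empty one would be a real loss, and clearer wording would cost a few sentences and no new data.

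Part of this stands. The label is loose, the phrase about training sessions is at odds with the timetable and with section 5.1, and the status of the 50-minute block is not stated.

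The step from there to a measure that does not work fails. Section 6.2 says what the measure is computed from, and that source leads to the case block. Cases completed can be read off the same record, so a fast participant and an unfinished one are distinguishable. The training phrase sits in a sentence about sending meeting links and defines no measure.

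The stop question is conditional on a rule the plan does not contain. Kaplan-Meier summaries and censoring rules would add little in a descriptive study of about 30. With one common stop, such an estimate differs from the simple percentage finishing only through technical losses.

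**Conclusion.** No change is called for. This is an undefined term that an analyst fills sensibly from the sentence in which it stands, together with one clerical inconsistency about training. Followed as written, section 6.2 gives the time for the case block, planned at 50 minutes for 10 cases, and not the 90-minute call. The effect on time per case and on the section 7 descriptives is nil. The effect on the second measure is at most the gaps between cases, according to whether span or sum is taken.

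The conclusion assumes that the data source named in section 6.2 governs the meaning of the measure, and that times are read alongside the number of cases completed. It also assumes that incomplete sessions are few or visible as such. The 3 to 5 opening sessions in section 3 are where the timing boundaries and the adequacy of 50 minutes would show themselves. If many participants could not finish 10 cases, means over completed cases would need care in interpretation, but the documents give no grounds for putting a size on that.

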6.3 To assess the mental effort required with using NAVIFY Oncology Hub

The mental effort required to prepare each individual case will be measured subjectively in the Post-Simulation survey using the **NASA Task Load Index (NASA TLX)**. This 6-item multi-dimensional scale assesses mental demand, temporal demand, performance, effort and frustration. We recommend the use of this measure because it has been well-validated (Hart, 2006) and used widely across a number of domains, including research on those in the medical community (Hoonakker et al. 2011; Mazur et al. 2012; Ruiz-Rabelo et al. 2015; Sartang et al. 2017; Young et al. 2008). It has been specifically designed to assess the workload associated with a given task, one of the key objectives of this study.

6.4 To gather feedback on the study methods

As clinical simulation is a relatively novel methodology to assess digital health technologies, additional questions on the use of clinical simulation will be put to participants on the Post-Simulation Survey. Example questions/topics include:

- How **similar the cases were to the cases the participant typically prepares** in their day-to-day practice in terms of complexity, demographics, information available, prognosis, etc.?
- How similar was this task to tasks you complete during a typical week?
- How difficult did this task seem to you? What made it more or less difficult?

On the Post-Simulation Survey, additional questions will be asked to provide useful information about each oncologist's clinical experience and familiarity with digital solutions. For example, how many patients the participant typically sees each week, how many many years the participant has spent as part of a tumor board in their career, what information they typically review before seeing a patient, what solutions/technologies the participant might use to prepare for consultations and collaborate with colleagues. See the full Post-Simulation Survey at Appendix A.

7. ANALYSIS

Thematic analysis of interview outputs will be performed by reviewing recordings from study participants in Phase 1. This analysis seeks to validate potential benefits and use cases for NAVIFY Oncology Hub, especially in areas such as accessing cancer patient data, care coordination, cognitive burden and shared decision-making.

Data from the simulation sessions will involve calculating summary descriptives (e.g., means and percentages) on case-specific endpoint measures. Counts or percentages may also be calculated on tabulated responses to survey questions to determine whether certain themes regarding the study participants' participation experience prove common across the participants and, therefore, warrant attention.

8. **REGULATORY ISSUES**

